6. INCLUSION AND EXCLUSION CRITERIA*

Inclusion Criteria:

- Age greater than 18 years old

INVESTIGATOR STUDY PLAN - H00015196

- New onset of hematemesis, melena or hematochezia
- Able to sign consent
- Hemodynamically stable (i.e. blood pressure >100/60 or pulse <110 at the time of consent)
- ED must plan to admit patient to the hospital or Clinical Decision Unit.
- If patients have pacemakers and/or ICD they will be placed on telemetry.

Exclusion criteria:

- Adults unable to consent
- Individuals who are not yet adults (infants, children, teenagers)
- Pregnant women
- Prisoners
- Prior history of gastroparesis
- Prior history of gastric, or small bowel surgery
- Prior history of inflammatory bowel disease
- Concern for infectious colitis
- Evidence of dysphagia at the time of presentation
- Presence of small amounts of bright red blood per rectum
- Allergy to metoclopramide or erythromycin
- Code status of DNR/DNI or CMO
- Prior history of abdominal radiation
- Abdominal pain suggesting an acute abdomen or obstruction. In clinical practice, only patients with crampy abdominal pain due to Crohn's disease, previous intestinal surgery and a previous history of radiation therapy require a patency capsule or CT enterography, before capsule endoscopy.
- Patients who cannot undergo surgery

Subjects who do not speak English may be included if an IRB-approved short form is available for use in their language and interpretation services are available.

7. **STUDY-WIDE NUMBER OF SUBJECTS***

See #25.

8. **STUDY-WIDE RECRUITMENT METHODS***

See #24.

9. **STUDY TIMELINES***

- The participation of individual subjects in this study will be approximately 31-40 days (the length of their hospitalization plus an additional thirty days for follow up).
- The duration anticipated to enroll all study subjects is about 24 months.

INVESTIGATOR STUDY PLAN - H00015196

- The estimated date for the investigators to complete this study and for data analysis is 3 years.

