11. PROCEDURES INVOLVED*

Screening

- Patients presenting to the Emergency Room with H or NHGIB (defined as hematemesis, or melena or hematochezia respectively or severe anemia) will be identified by a member of the ED staff and triaged to the CDU for stable patients or ICU for unstable patients.

Once a subject is identified a page will be sent to a member of the research team (i.e, research staff member, GI fellow on call, or GI attending on call) from the CDU. In addition to this, the clinical research coordinator and or GI fellow will screen the Emergency Department triage software for patients who are listed as having NHGIB. Based on prior experience of our randomized trial we expect for every 3 patients asked to participate in the study, there will be 1 patient who agrees to participate. In the Emergency Department study already cited, the Emergency Department at UMass sees about 350 patients annually for GI bleeding. Of these patients, approximately 230 patients have NHGIB and 120 have hematemesis. Given the 3:1 screening ratio, we would expect approximately 40 to be enrolled for the H and 40 patients for the NHGIB patients every year who agree to participate in the study. In 24 months, we would expect to recruit up to 160 patients to our study, 80 for the H and NHGIB respectively. Once a subject is identified the subject will then be seen and examined by the GI fellow and attending as per standard of care and asked to participate in the study.

[figure not shown]
Randomization:

- If inclusion/exclusion criteria are met, the consent discussion takes place and only if the subject agrees and consent is obtained, then the subject is randomized to the “Early Capsule Group” or “Standard of Care Group.” All patients in the “Early Capsule group” will receive the video capsule. A few of the patients in the “Standard of Care Group” may receive the capsule as indicated by what is considered the standard workup.

INVESTIGATOR STUDY PLAN - H00015196

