24. LOCAL RECRUITMENT METHODS

As mentioned in Section 11, subjects with H and NHGIB will be identified by a member of the Emergency Department staff, CDU staff or one of the study staff members. Based on prior experience of our randomized trial we expect for every 3 patients asked to participate in the study, there will be 1 patient who agrees to participate. In the emergency department study already cited, the Emergency Department at UMass sees about 350 patients annually for GI bleeding. Of these patients, approximately 230 patients have NHGIB and 120 have hematemesis. Given the 3:1 screening ratio, we would expect approximately 40 to be enrolled for the H and NHGIB patients every year who agree to participate in the study. In 24 months, we would expect to recruit up to 160 patients to our study, 80 for the H and NHGIB respectively. Once a subject is identified the subject will then be seen and examined by the GI fellow and attending as per standard of care and asked to participate in the study. They will be offered an opportunity to ask any questions they have regarding this study. Subjects will be notified of the risks and benefits of participating in this study. They will not be offered financial compensation for their participation. No identifying information will be collected for study purposes until patient has agreed to participate in the study. Any identifying information obtained after enrollment in the study will be de-identified/de-linked from the subject as described above.

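### The hematemesis forecast of 80 patients in 24 months holds only if every hematemesis presenter is eligible and asked, and the added triage-software screen does not name hematemesis

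*Protocol*

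**What the plan says.** Protocol Section 11 (Screening) sets out the forecast, and Sections 24 and 25 repeat it.

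- **Consent ratio:** "for every 3 patients asked to participate in the study, there will be 1 patient who agrees to participate".
- **Supply:** "the Emergency Department at UMass sees about 350 patients annually for GI bleeding", of whom "approximately 230 patients have NHGIB and 120 have hematemesis".
- **Forecast in Section 11:** "we would expect approximately 40 to be enrolled for the H and 40 patients" for NHGIB each year, giving up to 160 patients in 24 months, 80 in each group.
- **Forecast in Sections 24 and 25:** "we would expect approximately 40 to be enrolled for the H and NHGIB patients every year". This can be read as 40 combined, although the same sections also expect 80 per group in 24 months.
- **Accrual period (Section 9):** "The duration anticipated to enroll all study subjects is about 24 months". Completion of the study and data analysis is put at 3 years.
- **Extra screen (Section 11):** the coordinator or fellow "will screen the Emergency Department triage software for patients who are listed as having NHGIB". Hematemesis is not named there.

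Section 11 sends unstable patients to the ICU rather than the CDU, and allows the consent discussion only after the entry criteria are met. Section 6 lists those criteria. They include stability, ability to consent, a planned admission, and exclusions for prior gastric or small bowel surgery, dysphagia, code status and prior abdominal radiation. No eligible fraction is given for either group. Section 25 describes the forecast as consistent with the power calculations.

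**The concern.** The ratio is defined on patients asked but is applied to patients presenting. For H this leaves no allowance for patients who are ineligible, unstable or missed. For NHGIB the same division gives nearly twice the stated number, so the two forecasts of 40 do not come from one visible rule.

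The two groups are randomized separately, and each is sized at 40 per arm, so a surplus of NHGIB patients cannot make up for a shortage of H patients. Section 13 explains the step from 36 to 40 per arm as cover for technical failures and incompletely studied patients. It is not an allowance for slow accrual. If H accrues more slowly than forecast, either the H comparison is made on fewer patients than planned or the trial runs past its stated timeline. The group with no slack in its forecast is also the one left out of the active software screen.

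**Working it through.** **Inputs from the Protocol.** Presenters per year: H 120, NHGIB 230. Asked to agreeing: 3:1. Accrual: 24 months. Planned size: 80 per group. Not given: the share s of presenters who are eligible and asked.

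**Formula.** Enrolled per year = presenters × s / 3.

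**Step 1: reproduce the stated figures.**
- H with s = 100%: 120 / 3 = 40 a year, and 2 × 40 = 80 in 24 months. This matches the plan exactly.
- NHGIB with s = 100%: 230 / 3 = 76.7 a year, and 2 × 76.7 = 153 in 24 months. The plan states 40 and 80.
- The share at which NHGIB gives 40 a year is 40 × 3 / 230 = 52%.

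**Step 2: break-even shares for H.**
- 80 in 24 months needs s = 80 / 80 = 100%.
- 72 in 24 months (36 per arm) needs s = 72 / 80 = 90%, with nothing left for technical failures.
- 80 in 36 months needs (80 / 3) / 40 = 67%.

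**Step 3: H accrual over a range of s (assumed).** Months to 80 = 12 × 80 / (40 × s).

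| s | H per year | H in 24 months | Months to 80 |
|---|---|---|---|
| 100% | 40 | 80 | 24 |
| 90% | 36 | 72 | 26.7 |
| 80% | 32 | 64 | 30 |
| 60% | 24 | 48 | 40 |
| 52% (scenario: the NHGIB break-even share) | 20.9 | 42 | 46 |
| 50% | 20 | 40 | 48 |

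**Step 4: illustrative power for H.** The Protocol gives no alpha, sidedness or power target. I assume two-sided 0.05 and borrow the hazard ratio of 2.7 from the earlier NHGIB trial. Schoenfeld: power = Φ(√d × ln(2.7) / 2 − 1.96), where d is the number of events. An event fraction of 45% is the mean of the 63% and 27% detection rates in that trial (Section 5).
- 80 patients: d = 36, power 85%.
- 72 patients: d = 32.4, power 81%.
- 64 patients: d = 28.8, power 76%.
- 48 patients: d = 21.6, power 64%.
- 42 patients: d = 18.8, power 58%.
- 42 patients with 60% events (assumed): d ≈ 25, power about 70%.

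Comparing proportions of 63% and 27% instead gives 91% at 40 per arm, 88% at 36 and 66% at about 21.

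**The case against.** **NHGIB may not have been discounted.** A reader might infer that the plan cuts NHGIB by half for eligibility and that H must suffer the same cut. The documents do not say so. Section 11 plans 80 per group and up to 160 in all, so 40 a year for NHGIB may be a cap at the number needed. Nor need the two groups share one eligible fraction: some exclusions, such as small amounts of rectal blood or suspected infectious colitis, fall mainly on NHGIB. This stands. It makes the 52% share, with its 42 patients and 46 months, one scenario and not a forecast. It does not rescue the H figure, which needs 100% whatever the NHGIB number means.

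**The ratio may already include eligibility.** The Protocol also calls it a screening ratio. If that means screened to enrolled, 40 for H would be net of exclusions. But the text defines the ratio on patients asked, and on the other reading uncapped NHGIB would still be 77. The ambiguity needs resolving in the text.

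**H has other routes in.** It would be wrong to say that H relies on staff pages alone. Section 24 has ED, CDU or study staff identifying patients of both kinds, and the NHGIB-only wording may be an oversight. The gap is the missing backstop only.

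**H need not close underpowered.** No rule stops H accrual at 24 months. The DSMB charter (Section 6) provides for recruitment reports and at least two meetings a year, so a slow group would be noticed. Overrun is as plausible as a small sample. The power figures also borrow NHGIB inputs, and the 63% and 27% rates are for active bleeding, whereas the primary endpoint also counts stigmata of recent bleeding. Events could therefore be more frequent than 45%.

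**Conclusion.** The point holds as a flaw in the accrual forecast. The stated 80 H patients in 24 months follows from the Protocol's inputs only if every H presenter is eligible and asked, which its own entry criteria and ICU routing exclude. Some shortfall at 24 months therefore follows from the documents, on the ratio as they define it. Its size does not. It depends on a share they do not give: 8 patients short at 90%, 16 at 80%, 32 at 60% and 40 at 50%. Below a share of about two thirds, 80 H patients would not be reached even in 36 months of accrual, the whole period allowed for completing the study and its analysis.

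A reader might go further and conclude that H will probably fall far short, at about 42 patients and 58% power. The documents do not support that as a prediction. It rests on treating the NHGIB forecast as an eligibility discount, carrying that discount to H, and borrowing an NHGIB hazard ratio with an assumed event fraction. At 90% H would reach 72, with illustrative power of about 81%.

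The issue is one of feasibility and of a stated planning figure. It does not affect the estimand or the analysis method, but it is worth correcting because the plan ties the forecast to its power statement.

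**What to change.** - **Section 11:** add hematemesis to the existing triage-software screen, or explain why it is left out.
- **Sections 11, 24 and 25:** state the assumed eligible-and-asked share for each group, say whether the 3:1 ratio is per patient asked or per patient screened, and recompute both forecasts. If the NHGIB figure is a cap at the planned 80, say so.
- **Sections 24 and 25:** write 40 for each group, if that is what is meant.
- **Sections 9 and 25:** give the expected H size at 24 months, or the time to reach 80, as a range like the one above. Show the 52% share, if at all, as a labelled scenario. State what happens to H accrual and the H analysis if 80 is not reached in about 24 months.
- **Section 13:** label any H power figure as illustrative, and state the hazard ratio, event fraction and alpha it assumes.

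The cost is some Protocol wording, one more condition in a screen already planned, and a less favourable stated forecast for H. No increase in enrolment is asked for.

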10. STUDY ENDPOINTS*

- The primary endpoint will be time to detection of active bleeding or stigmata of recent bleeding [blood clot or visible vessel].
- Secondary endpoints will include, admission rate, hospital length of stay, number of invasive procedures, blood product transfusions, number of therapeutic procedures, complication rates, costs of admission, and readmission rates

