The PI or sub-investigator will then view the video of the capsule recording [it takes about 5 minutes to establish if there is bleeding and where it is coming from. More detailed analysis will take about 15-20 minutes]. As soon as the capsule recording has been reviewed, the PI or sub-investigator will inform the patient's attending gastroenterologist on the consult service as to where the bleeding is coming from or that bleeding is not seen, as soon as possible after the video has been reviewed. Depending on the findings a recommendation will be made as to the next most appropriate test. See attached Figure 1. If blood is found in the esophagus, stomach or duodenum an upper endoscopy is recommended. If blood is seen in the small intestine, it will be recommended that the subject next have a push enteroscopy, deep enteroscopy, or angiography. If blood is found in the right colon, colonoscopy may be performed or deferred to colonoscopy as an outpatient, if active bleeding has ceased. If the capsule study is not diagnostic and no blood is seen in the GI tract and there is no ongoing hematochezia, the subject will be placed in ED observation for up to 23 hours and evaluated for potential discharge and follow-up by gastroenterology as an outpatient. If, and as appropriate an EGD or colonoscopy will be performed as an outpatient within 72 hours.

For most subjects, the capsule will pass in a bowel movement within 24 -72 hours of ingestion.

An equal number of subjects [up to 40] will be randomized to the "SOC group." For NHGIB workup may include upper endoscopy, colonoscopy, and additional capsule or small bowel enteroscopy depending on the subject's presentation and the results of the workup performed by the gastroenterology team. For some subjects, the VCE would be done as part of standard of care. We estimate that 4-10% of patients will have small intestinal bleeding. For patients requiring a video capsule endoscopy as part of "SOC workup" the patients will be given the same Olympus video capsule that is used in the "Early Capsule" group. Further management would be as standard of care which requires

INVESTIGATOR STUDY PLAN - H00015196

admission. These subjects will be discharged on the recommendation of the attending hospitalist after completion of treatment.

Review and Follow-Up

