During hospitalization, data will be recorded from ED pulse check, and EPIC regarding fluid administration, transfusion of pRBC, initial hematocrit, times and types of procedures (e.g. upper endoscopy, enteroscopy, colonoscopy etc), time from entry to ED and CDU, to time to localization of source of bleeding, admission disposition discharge from CDU, regular floor, ICU), time of discharge. The procedures involved in the hospitalization (i.e. upper endoscopy, enteroscopy, and colonoscopy) will be done as part of standard of care. All of this information will be linked to the subject's study ID number as described above. This data collection is for research purposes only.

In addition, the costs of the procedures will be collected through financial services. The costs that will be collected are both the fixed and variable costs associated with each patient in the study. We will also collect the direct and indirect costs allocated to each patient. All charges associated with the admission for each patient in the study will have costs allocated. This will be evaluated as an additional data point to compare the two arms of the study. No additional PHI will be collected.

Telephone Follow-Up

Those subjects discharged from the CDU will be contacted the following day by phone by a research staff member to make sure that they are doing well and that the appropriate follow up procedure has been arranged. Each patient will be called 30 days after discharge to check to see if bleeding has recurred. Please see attached form for telephone script that staff member will read along with particular questions that will be asked.

No more than three attempts will be made at each time point to reach the subject. If a message is left, it will be "Hello, this is [name] calling from UMass looking to speak with [subject]. Please call back at [number] at your earliest convenience. Thank you."

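### The primary endpoint has no common observation window or censoring rule: its timing data are tied to the hospital stay, which ends by a discharge decision that may differ by arm

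*Protocol*

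**What the plan says.** **Endpoint.** Protocol Section 10: "The primary endpoint will be time to detection of active bleeding or stigmata of recent bleeding". Clot and visible vessel are given as the stigmata. No time limit is attached.

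**Collection.** Section 11 (Review and Follow-Up) begins its data list with "During hospitalization, data will be recorded from ED pulse check, and EPIC". The list includes times and types of procedures and "time from entry to ED and CDU, to time to localization of source of bleeding". Section 13 says that data come from medical-record review, names time to detection among them, and plans a Kaplan-Meier comparison. It gives no censoring rule.

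**Disposition.** Under Section 11, a patient with a non-diagnostic capsule, no blood seen and no ongoing hematochezia is observed for up to 23 hours and considered for discharge. Then, where appropriate, "an EGD or colonoscopy will be performed as an outpatient within 72 hours". For SOC patients, who are to be admitted, Section 11 says: "These subjects will be discharged on the recommendation of the attending hospitalist after completion of treatment". Section 4 likewise admits the whole SOC group and lets stable capsule patients leave from the CDU. Section 5 (Background) and Section 29 speak of discharge without admission in terms that cover both groups.

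**After discharge.** Section 9 keeps each patient in the study for the stay plus thirty days. Patients discharged from the CDU get a next-day call about how they are and whether follow-up is arranged. Then: "Each patient will be called 30 days after discharge to check to see if bleeding has recurred".

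**SAP.** The document filed as the SAP is the DSMB charter. Its Section 9 says that a SAP will define the calculated variables, but it contains no such definition for this endpoint.

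**The concern.** A time-to-event endpoint needs a stated end of observation that does not depend on the treatment received. Here the passage that describes capture of the time ties it to the hospital stay. The stay can end early after a negative capsule, which is a post-randomisation result available early in only one arm by design.

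A stigma first seen at a deferred outpatient endoscopy fits the Section 10 definition of an event, yet nothing says that it is to be recorded or counted. Two abstractors could follow this protocol faithfully and produce different primary data: one stops at discharge, the other reads on into outpatient records.

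The analysis then has two poor options for patients who leave undetected:

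- If they are carried as never detected, detections that did occur are missed.
- If they are censored at discharge, Kaplan-Meier assumes that they would be detected at the same rate as those kept in hospital. Discharge was decided partly because the capsule was negative, so that censoring is informative.

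Either choice can distort the comparison that the trial exists to make.

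**Working it through.** The plan states no window, no censoring time and no expected number of outpatient detections, so there is no figure of its own to reproduce. The check sets the provisions side by side and then sizes the exposure under stated assumptions.

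**1. Who is exposed.** The exposed patients are those who leave without a detection and are examined later. In the capsule arm these are patients with a non-diagnostic capsule. A later first detection is plausible. Section 5 describes the capsule's reach as esophagus to right colon. Section 11 stops the recording at the cecum in NHGIB and after small-bowel entry in H. A colonoscopy deferred because blood was seen in the right colon is not exposed, since the capsule has already made the detection.

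**2. How many, capsule arm, per bleeding group.** Inputs:

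- n = 40 per arm (Section 13).
- d = 30% discharged undetected. This is an assumption: it is the share dischargeable in the hematemesis trial cited in Section 5, carried over to NHGIB.
- q = 10% to 50% of those with a first detection at outpatient endoscopy. This is an assumption without a source in the documents.

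Discharged undetected: 40 × 0.30 = 12. Detections at risk: 12 × 0.10 = 1.2 to 12 × 0.50 = 6.0. Letting d run from 10% to 37% (37% is 1 minus the 63% prior capsule rate in Section 5) gives 40 × 0.10 × 0.10 = 0.4 to 40 × 0.37 × 0.50 = 7.4.

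**3. Direction, capsule arm only.** Assume 55% are detected before any discharge, 30% are discharged undetected and 15% stay undetected. Let h = 30% to 60% be the later in-hospital yield. The 55% and h are also assumptions.

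| Handling of discharged patients | Estimated detection | Range | Error against full capture |
|---|---|---|---|
| Full capture | 0.55 + 0.30q + 0.15h | 62.5% to 79.0% | none |
| Counted as undetected | 0.55 + 0.15h | 59.5% to 64.0% | −0.30q = −3 to −15 points |
| Censored at discharge | 1 − 0.45(1 − h) = 0.55 + 0.45h | 68.5% to 82.0% | 0.30(h − q) = −6 to +15 points |

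For the last row, h = 0.60 and q = 0.10 give 0.30 × 0.50 = +15 points. With h = 0.30 and q = 0.50 the result is 0.30 × (−0.20) = −6 points. The sign depends on the handling and on yields that the plan does not give.

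**4. Effect on power in one case.** Take the prior rates of 63% and 27% (Section 5), 40 per arm and two-sided alpha 0.05 (assumed, as none is stated). Power for two proportions is 0.914. If 63% is the complete capsule rate, d = 30%, and only the capsule arm loses detections, the observed rate is 0.63 − 0.30q. That is 60.0%, 54.9% or 48.0% at q = 10%, 27% or 50%, with power 0.860, 0.726 or 0.492. If 63% is already an in-hospital rate, this reduction does not apply. These are proportion-scale figures, not a time-to-event result.

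**The case against.** A reader might infer that detection times are collected solely in hospital, that post-discharge detections are lost, and that this happens in the capsule arm alone. The documents do not support that reading.

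- **Collection is not said to stop at discharge.** Section 13's record review has no stated end, Section 27 gives access to Epic and Provation without one, and Section 9 adds thirty days. Readmission is a secondary endpoint that cannot come from the index stay, so the Section 11 list is not exhaustive. An outpatient endoscopy at the same centre could be found. This stands: loss is possible, not shown. It does not supply a window, a censoring rule or a statement that such findings count.
- **The call may ask more than recurrence.** Section 11 refers to an attached script that is not among the documents. Nothing should be concluded about questions it may contain.
- **SOC patients may be affected too.** Sections 5 and 29 conflict with Section 4 on who may be discharged. Section 5 also reports that nearly 30% of admitted patients at this site had no inpatient endoscopy. One-sided loss is therefore not established. The window still depends on disposition, now possibly in both arms, and the net bias is unknown.
- **The sizes rest on assumptions.** The 55%, q and h have no source, the 30% comes from hematemesis, and only the capsule arm is modelled. The range of −15 to +15 points is thus not an error in the treatment comparison. This stands in full.
- **A later SAP may define the variable.** The charter promises one. That could settle the analysis rule, but it cannot recover findings that nobody was told to collect.

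**Conclusion.** The point holds as a gap in the definition of the primary endpoint. The plan sets no common observation window and no censoring rule, does not say whether outpatient findings count, and ties the recorded times to a stay whose end depends on disposition. If discharge differs by arm, as Section 4 indicates, the Kaplan-Meier comparison can be biased through missed detections or informative censoring. The plan does not determine the direction, so the effect cannot be called conservative.

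The exposure is about 1 to 6 first detections per group of 40 capsule patients. That assumes 30% leave undetected, 10-50% of them have stigmata at outpatient endoscopy, and none of those findings is captured. A stronger conclusion, that events will be lost in the capsule arm alone, is not supported. The gap should be closed because it concerns the primary endpoint and a short text change removes it.

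**What to change.** Amend Sections 11 and 13 of the protocol, and carry the same text into the SAP that the charter promises:

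1. Record the date, time and findings of every endoscopy and capsule study, inpatient or outpatient, in both arms, up to one fixed horizon from randomisation (for example 30 days). Use Epic and Provation, plus one question on procedures done elsewhere in the existing 30-day call. That call is timed from discharge, so it falls no earlier than day 30 from randomisation for a patient discharged after randomisation.
2. Count the first detection within the horizon as the event wherever it is made. Censor undetected patients at the horizon or last contact, not at discharge.
3. Use one term for the endpoint. Section 10 speaks of detection, Section 11 of localization and Section 13 of diagnosis.
4. Reconcile Sections 4, 5 and 29 on which patients may be discharged without admission. Which rule applies is for the investigators to decide.

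Cost: one record look-up and one call question for up to 160 patients (40 × 2 arms × 2 groups), with no new visit, staff or procedure.
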